4.6.5 Drug Concentration Measurements

Complement levels (C3, C4, C1INH-Function, and C1INH % activity) will be measured during the first week of the study period.

4.7 Data Quality

Monitoring and auditing procedures defined/agreed by the sponsor will be followed, in order to comply with Good Clinical Practice (GCP) guidelines. Our center will be monitored at quarterly to ensure compliance with the study protocol, GCP and legal aspects. This will include on-site checking of the case report forms (CRF) for completeness and clarity, cross checking with source documents, and clarification of administrative matters.

4.8 Documentation

Entries made in the CRF must be either verifiable against source documents, or have been directly entered into the CRF, in which case the entry in the CRF will be considered as the source data. The source data parameter to be verified and the identification of the source document must be documented. The study file and all source data should be retained until notification given by the sponsor for destruction.

5 Ethical And Legal Aspects

5.1 Ethics Committee (EC) Or Institutional Review Board (IRB)

Documented approval from appropriate Ethics Committee(s)/IRBs will be obtained prior to study start, according to GCP, local laws, regulations and organizations. When necessary, an extension, amendment or renewal of the Ethics Committee approval

must be obtained and also forwarded to the sponsor. The Ethics Committees must supply to the sponsor, upon request, a list of the Ethics Committee members involved in the vote and a statement to confirm that the Ethics Committee is organized and operates according to GCP and applicable laws and regulations.

5.2 Ethical Conduct Of The Study

The procedures set out in this protocol, pertaining to the conduct, evaluation, and documentation of this study, are designed to ensure that the sponsor and investigator abide by GCP Guidelines and under the guiding principals detailed in the 1989 version of the Declaration of Helsinki. The study will also be carried out in keeping with applicable local law(s) and regulation(s). This may include an inspection by the sponsor representatives and/or Regulatory Authority representatives at any time. The investigator agrees to the inspection of study-related records by the Regulatory Authority/sponsor representatives, and must allow direct access to source documents to the Regulatory Authority/sponsor representatives.

Modifications to the study protocol will not be implemented by either the sponsor or the investigator without agreement by both parties. However, the investigator may implement a deviation form, or a change of, the protocol to eliminate an immediate hazard(s) to the trial subjects without prior EC/IRB/Sponsor approval/favorable opinion. As soon as possible, the implemented deviation or change, the reasons for it and if appropriate the proposed protocol amendment should be submitted to the EC/IRB/Sponsor. Any deviations from the protocol must be fully explained and documented by the investigator.

5.3 Regulatory Authority Approvals/Authorizations

Regulatory Authority approvals/authorizations/ notifications, where required, must be in place and fully documented prior to study start.

5.4 Subject Information And Consent

A core information and Informed Consent Form will be provided. Prior to the beginning of the study, the investigator must have the EC/IRB written approval/favorable opinion of the written Informed Consent Form and any other written information to be provided to subjects. The written approval of the EC/IRB

together with the approved subject information/Informed Consent Forms must be filed in the study files.

Written informed consent must be obtained before any study specific procedure takes place. Participation in the study and date of informed consent given by the subject should be documented appropriately in the subject's files.

5.5 Confidentiality

All records identifying the subject will be kept confidential and, to the extent permitted by the applicable laws and/or regulations, will not be made publicly available.

Subject names will not be supplied to the sponsor. Only the subject number and subject initials will be recorded in the case report form, and if the subject name appears on any other document (e.g., pathologist report), it must be obliterated before a copy of the document is supplied to the sponsor. Study findings stored on a computer will be stored in accordance with local data protection laws. The subjects will be informed in writing that representatives of the sponsor, EC/IRB, or Regulatory Authorities may inspect their medical records to verify the information collected, and that all personal information made available for inspection will be handled in strictest confidence and in accordance with local data protection laws.

If the results of the study are published, the subject's identity will remain confidential.

The investigator will maintain a list to enable subjects' records to be identified.

- 6 Statistical Methods And Determination Of Sample Size
- 6.1 Statistical And Analytical Plans
- 6.2 Determination of Sample Size

The sample size calculations were based on a conservative assessment aimed to show $\sim 50\%$ reduction in DGF rates with C1INH application. Data from the Cedars-Sinai Medical Center Renal Transplant Program for DGF rates are shown below:

CONFIDENTIAL

	Transplants 7/1/2011 until 7/1/2013
	N=237
	DGF Rate
ECD	27/36 (75%)
DCD	9/13 (69%)
Final Cr >/=1.5	28/37 (76%)
Non-ECD/DCD/Cr<1.5	33/100 (33%)

Briefly, the DGF rates at our center for the proposed study groups are >70% compared to 33% for SCD donors. Thus, a conservative proposal is explored below. The sample size calculations showing 35 subjects per group would sufficiently power the study (80%) to show 50% reduction when an anticipated DGF rate of 50% for the study group is anticipated.

The "proportion" below is the proportion with DGF. A 2-sided test (to be more conservative) was performed. We assumed a 50% DGF rate in the Placebo group. Treated group DGF rate vary: 20%, 25%, and 30%. sample size per group for 80% and 90% power are shown.

Two group continuity corrected χ^2 test of equal proportions (odds ratio = 1) (equal n's)

-	1	2	3	4	5	6
Test significance level, \Box	0.050	0.050	0.050	0.050	0.050	0.050
1 or 2 sided test?	2	2	2	2	2	2
Treated Group	0.200	0.250	0.300	0.200	0.250	0.300
proportion, π_1 Placebo Group	0.500	0.500	0.500	0.500	0.500	0.500
proportion, π_2 Odds ratio,						
$\psi = \pi_2 (1 - \pi_1) / [\pi_1 (1 -$	4.000	3.000	2.333	4.000	3.000	2.333
π_2)]						
Power (%)	80	80	80	90	90	90
n per group	45	66	103	58	85	134

A two group continuity corrected χ^2 test with a 0.05 two-sided significance level will have 80% power to detect the difference between a Treated Group proportion, π_1 , of 0.20 and a Placebo Group proportion, π_2 , of 0.50 (odds ratio of 4.00) when the sample size in each group is 45.

Two group continuity corrected χ^2 test of equal proportions (odds

Note: The odds ratio (OR) is the OR for DGF. In Column 1, OR = 4, so the odds of DGF in the Placebo group is 4 times the odds of DGF in the Treated group.

One-sided tests:

proportion, π_1

 π_2)

ratio = 1) (equal n's)						
	1	2	3	4	5	6
Test significance level, \Box	0.050	0.050	0.050	0.050	0.050	0.050
1 or 2 sided test?	1	1	1	1	1	1
Treated Group	0.200	0.250	0.300	0.200	0.250	0.300

Placebo Group	0.500	0.500	0.500	0.500	0.500	0.500
proportion, π_2 Odds ratio,						
$\psi = \pi_2 (1 - \pi_1) / [\pi_1 (1 -$	4.000	3.000	2.333	4.000	3.000	2.333

 Power (%)
 80
 80
 80
 90
 90
 90

 n per group
 37
 54
 83
 48
 71
 111

Statistical Assumptions

- Since this study is a Phase I/II, we will primarily explore the safety of the proposed dose in the renal transplant population receiving high-risk ECD and DCD kidneys. Our previous experience in a population of highly-HLA sensitized renal allograft recipients showed that administration of 20U/kg (8 doses in 1 month) was safe and without AE or SAE when compared to placebo (NCT01134510). Based on the calculations above, we propose a randomized, placebo controlled trial of C1INH vs. placebo entering 35 eligible patients into both arms of the study.
- 7 Adverse Events (AEs)
- 7.1 Adverse Event (AE) Monitoring
- 7.2 Adverse Event (AE) Definitions
- 7.2.1 Adverse Events (AEs)

An AE is any untoward medical occurrence in a subject or clinical investigation subject administered with a pharmaceutical product. The AE does not necessarily have to have a causal relationship with this treatment. An AE can therefore

be any unfavorable and unintended sign (including an abnormal laboratory finding), symptom, or disease temporally associated with the use of an investigational product, whether or not considered related to the medicinal product.

Adverse events associated with the use of a drug in humans, whether or not considered drug related, include the following:

- An AE occurring in the course of the use of a drug product in professional practice,
- An AE occurring from an overdose whether accidental or intentional,
- An AE occurring from drug abuse,
- An AE occurring from drug withdrawal.
- An AE where there is a reasonable possibility that the event occurred purely as a result of the subjects participation in the study (e.g. adverse event or serious adverse event due to discontinuation of antihypertensive drugs during wash-out phase) must also be reported as an adverse event even if it is not related to the investigational product.

The clinical manifestation of any failure of expected pharmacological action is not recorded as an AE if it is already reflected as a data point captured in the CRF. If, however, the event fulfills any of the criteria for a "serious" AE (SAE), it must be recorded and reported as such.

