Over the past decade, improvements in immunosuppressive regimens, surgical techniques, and organ procurement have resulted in a significant increase in renal transplantation success (Oniscu et al, 2005). Currently, the worldwide rates for 1- and 5-year graft survival are 95% and 80%, respectively, with death with a functioning graft being the most common reason for renal graft loss after 1 year (Daly et al, 2005). Studies on renal transplantation outcomes have traditionally focused on patient and graft survival, with little to no consideration of graft function (Boom et al, 2000). Although graft loss is the worst type of graft dysfunction, grafts with an impaired function require the most intense follow-up, are economically most costly and require rigorous clinical management to preserve life-expectancy of the graft (Boom et al, 2000). For these reasons, parameters of graft function are being increasingly included as outcome measures in renal transplantation studies, including delayed graft function (DGF). Indeed, the new UNOS allocation policies

(http://optn.transplant.hrsa.gov/policiesAndBylaws/policies.asp) scheduled for implementation in 2014 will tend to give higher risk kidneys to older diabetic recipients. This is likely to increase the risk significantly for DGF and poorer allograft function.

Despite a decline in the number of patients experiencing allograft rejection episodes over the past decade, the incidence of patients with DGF has remained steady and was reported in 2.6 percent of transplants from living donors, compared to 22, 28, and 41 percent of SCDs, ECDs, and donations after cardiac death patients respectively.

[figure not shown]

Figure 1: Data obtained from United States Renal Data Systems Report Transplantation 2012 Vol 2, pp 283-294.

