4.2.1 Inclusion Criteria

Recipient Inclusion Criteria

- 1). Adult men or women (18-70 years of age) who are on chronic dialysis therapy and acceptable candidates for kidney transplant.
- 2). Understand and sign a written informed consent prior to study specific procedures.
- 3). Recipients who are ABO compatible with donor allograft.
- 4). Recipients of kidney allograft from ECD* donors.
- 5). Recipients of kidney allograft from DCD** donors.
- 6). Recipients of kidney allograft other than ECD and DCD who have risk index of 3-8 (minimum 3 and maximum 8) for DGF, based on the criteria in the risk index detailed in Table 1.
- 7). Women of childbearing potential must have a negative pregnancy test prior to randomization, and must be on an acceptable form of birth control.

Table 1: Risk factors for Delayed Graft Function

Characteristic	Risk Index
Donor Age (years)	
<40	0
41-49	1
50-54	2
55-59	3
>60	6
Cold Ischemia time	
0-12	0
13-18	1
19-24	2
24-30	3
31-36	4
> 37	6
Recipient Race	
Non-Black	0
Black	1
Recipient with Diabetes	
Has Diabetes	1
No Diabetes	0
Donor cause of death due	
Donor age < 50 years	0
Donor age >50 years	3

*ECD Kidney: An ECD allograft is defined as a renal allograft donated for transplantation from a brain-dead donor over the age of 60 years or from a donor aged 50 to 60 years with two of the following: a history of hypertension, a pre-retrieval terminal serum creatinine greater than or equal to 1.5 mg/dl, or death from a cerebral vascular accident (stroke or aneurysm) (Cecka, 2004).

**DCD Kidney: Recovery of organs and or tissues from a donor whose heart has irreversibly stopped beating, previously referred to as non-heart-beating or asystolic donation (UNOS).

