4.5 Treatments

4.5.1 Treatments To Be Administered

This study is designed with two blinded treatment groups (C1INH vs. Placebo). Each group will include 35 patients in a treatment arm and 35 patients in a placebo arm.

This design is statistically powered to show significant differences if there is a 30--50% reduction in the treatment group and may trend towards positive treatment effect since extensive DGF (40--50%) is expected in ECD and DCD recipients. The dose of C1INH chosen is (50U/kg) (round to the nearest 500unit) X2 (high-dose treatment) which should increase serum C1INH levels significantly above physiologic levels. This is based on our observations from our experience using C1INH vs. placebo to prevent antibody-mediated rejection in humans. In those randomized to placebo, an equivalent volume of placebo (0.9%) normal saline) will be administered prior to graft reperfusion.

Patients who fulfill all I/E criteria will be enrolled into this Phase I/II study.

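### Section 6.2 supports its 50% placebo DGF rate with donor groups that do not match inclusion criteria 4-6, and 35 per arm gives 80% power only near the rate of those groups, not at 50%

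*Combined protocol and SAP*

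**What the plan says.** **Section 6.2** tabulates DGF at the centre from July 2011 to July 2013: ECD 27/36 (75%), DCD 9/13 (69%), final creatinine 1.5 or more 28/37 (76%), and a remaining row (neither ECD nor DCD, creatinine below 1.5) 33/100 (33%). It summarises: "Briefly, the DGF rates at our center for the proposed study groups are >70% compared to 33% for SCD donors". It then plans at a lower rate: "We assumed a 50% DGF rate in the Placebo group". It states that 35 per group gives 80% power for a 50% reduction from there.

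**Section 4.2.1, criteria 4-6** (and the synopsis) give three entry routes: ECD, DCD, and "Recipients of kidney allograft other than ECD and DCD who have risk index of 3-8 (minimum 3 and maximum 8) for DGF". Table 1 scores donor age, cold ischemia time, recipient race, recipient diabetes and donor cause of death. It does not score creatinine. A creatinine of 1.5 or more appears in the inclusion criteria only as one of the ECD sub-criteria, two of which are needed, for donors aged 50 to 60.

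**Section 4.5.1** says "extensive DGF (40--50%) is expected in ECD and DCD recipients".

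**Statistical Assumptions** (end of Section 6.2) describes the population as recipients of ECD and DCD kidneys and does not mention the index route.

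**The concern.** A planning rate can be called conservative only in relation to the patients who will be enrolled. One of the three groups cited for the rate above 70% has no entry route of its own, and one of the three entry routes has no row in the table. Two sections also give different expected DGF rates for the same ECD and DCD recipients. A reader therefore cannot tell whether 50% is low, about right or high for the kidneys the criteria admit.

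This matters because the power of 35 per arm depends strongly on the placebo rate. The trial reaches its advertised 80% for a halving of DGF only near the rate of the listed groups, and the index route may dilute that rate.

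**Working it through.** **1. Match the table rows to the entry routes.**

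| 6.2 row | DGF | Own route in criteria 4-6? |
|---|---|---|
| ECD | 27/36 (75%) | yes |
| DCD | 9/13 (69%) | yes |
| Final creatinine 1.5 or more | 28/37 (76%) | no |
| Neither, creatinine below 1.5 | 33/100 (33%) | partly, through index 3-8 |

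Two constructed cases, each with a non-ECD, non-DCD kidney and a non-Black, non-diabetic recipient:
- Donor aged 45, creatinine 1.2, cold ischemia 20 h scores 1 + 2 = 3. This is eligible, and the kidney belongs to the 33% row.
- Donor aged 45, creatinine 2.5, cold ischemia 18 h scores 1 + 1 = 2. This has no entry route, although the kidney belongs to the 76% row.

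**2. Pooled rates.** ECD and DCD: (27 + 9)/(36 + 13) = 36/49 = 73.5%. All three high rows, if they do not overlap: 64/86 = 74.4%. Section 4.5.1 puts ECD and DCD at 40-50%.

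**3. Reproduce the plan's own sample sizes.** The table is headed "Two group continuity corrected" chi-square test and reads "with a 0.05 two-sided significance level will have 80% power to detect the difference between a Treated Group proportion". With p1 treated, p2 placebo, d = p2 − p1 and p̄ their mean:

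n′ = [1.960·√(2p̄(1−p̄)) + 0.842·√(p1(1−p1) + p2(1−p2))]² / d²

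n = (n′/4)·[1 + √(1 + 4/(n′d))]²

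For 50% versus 25%, n′ = (1.342 + 0.557)²/0.0625 ≈ 57.7 and n ≈ 65.4, so 66 per group, as in the table. All 12 tabulated sizes reproduce. The sentence claiming 80% at 35 per group does not: a halving from 50% needs 66 (two-sided) or 54 (one-sided).

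**4. Power at 35 per arm for a halving of DGF.** Exact enumeration: sum Bin(i; 35, p/2)·Bin(j; 35, p) over all outcomes (i, j) for which the continuity-corrected chi-square is at least 3.841 (two-sided 5%).

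| Placebo DGF p | Treated | Power |
|---|---|---|
| 74.4% (three high rows) | 37.2% | 84% |
| 73.5% (ECD + DCD) | 36.7% | 82% |
| 50% (6.2 assumption) | 25% | 50% |
| 40% (lower end in 4.5.1) | 20% | 36% |

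**5. Effect of the index route.** Let w be its share of enrolment and r its DGF rate. The documents give neither, so both are assumed. Placebo rate p = (1 − w)·0.735 + w·r.

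| w | p if r = 33% | Power | p if r = 50% | Power |
|---|---|---|---|---|
| 25% | 63% | 67% | 68% | 73% |
| 50% | 53% | 54% | 62% | 65% |
| 75% | 43% | 40% | 56% | 57% |

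**6. Share at which 50% would be exact.** With r = 33%, w = (0.735 − 0.50)/(0.735 − 0.33) = 0.58.

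**The case against.** The strongest reply is that 6.2 does not calculate at more than 70%. Every column of its tables uses 50% on placebo, and by step 6 that allows about 58% of enrolment to come from kidneys with the contrast-row rate. This stands. A reader might infer that the trial was sized on a population it will not enrol, or that placebo DGF will fall below 50%. The documents support neither inference.

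Second, 33% is an average over the whole contrast row, including kidneys scoring 0-2. An index of 3-8 is meant to select the riskier part, so 33% is probably a floor for that route. This also stands, and it is why step 5 shows a second rate.

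Third, a reader might infer that high-creatinine kidneys are shut out. They are not: they can enter as ECD, as DCD or on the index. The 37 kidneys in that row are not a count of exclusions. The table does not say whether its rows overlap, and reading its creatinine label as donor terminal creatinine is reasonable but not stated.

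Fourth, other apparent discrepancies carry little weight. The rows total 186 of 237 transplants, but the table does not claim to be exhaustive. DCD at 69% against a claim of above 70% is trivial. The Introduction's rates ("compared to 22, 28, and 41 percent of SCDs, ECDs, and donations after cardiac death patients respectively") are national registry figures and need not match one centre.

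Finally, power of 50% at a 50% placebo rate comes from the sample-size arithmetic and would remain if the populations matched. That is correct. The two problems meet because the 80% claim is roughly true only at the rate of the listed groups, so both need one stated rate. Safety is the primary objective, which limits how much an efficacy case-mix point can weigh.

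**Conclusion.** The point holds as a failure of justification and internal consistency, not as proof that 50% is too high. The groups cited in 6.2 do not match criteria 4-6, the index route has no rate or share, and 4.5.1 and 6.2 disagree on ECD and DCD recipients (40-50% against 73%).

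The 80% power statement is wrong as written. For a halving of DGF, 35 per arm gives about 82-84% at 73-74% placebo DGF and about 50% at the stated 50%. These figures rest on the two-sided, continuity-corrected test named in 6.2 and on 35 evaluable patients in each arm. The diluted figures of about 67, 54 and 40% rest on the further assumption of 33% DGF on the index route. They illustrate sensitivity and are not forecasts.

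**What to change.** - Re-tabulate the 2011-2013 centre cohort in non-overlapping rows by actual entry route (ECD, DCD, neither with index 3-8), after applying the exclusions. State the expected share of each route.
- Reconcile 6.2, 4.5.1 and the Statistical Assumptions with criteria 4-6. Drop the creatinine row from the justification, or have the sponsor reconcile it with the criteria. Whether creatinine should be an entry route is an eligibility decision for the sponsor and is not settled by this point.
- Use one placebo DGF rate throughout, and call it conservative only if the re-tabulated mix supports that.
- Replace the 80% statement with the power that 35 per arm gives at that rate (about 50% for a halving if 50% is kept), and align the general power claims in 4.5.1 and 4.5.7.

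The cost is a re-tabulation of data the centre already holds and a rewrite of short passages in 4.5.1, 4.5.7 and 6.2. The downside is a less favourable stated power.

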NUMBER OF 70 patients will be enrolled into the
PATIENTS AND study (35 C1INH and 35 Placebo). The
CENTERS study will be initiated at Cedars-Sinai
Medical Center and extended to
collaborators with completion of
contractual agreements.
<pre>INVESTIGATOR / [name].</pre>
CLINICAL Cedars-Sinai Medical Center
TRIAL LOCATION

CONFIDENTIAL	C1INH	(Berinert®)	IRI	Study	in	Kidney	Transı	plant

CONFIDENTIAL	C1INH (Berinert®) IRI Study in Kidney Transplan
STUDY OBJECTIVES	 To evaluate and compare the safety of Berinert® 50U/kg in recipients of a kidney allograft from a high risk deceased donors receiving one IV dose of Berinert® 50U/kg (round to the nearest 500unit) or placebo preoperatively and a repeat dose (Berinert® 50U/kg v. Placebo) 24 hrs. post-transplant. To evaluate early kidney function in recipients of a kidney allograft from a high risk deceased donors following the administration of two IV doses of Berinert® pre-operatively and 24 hrs later as compared to placebo.
STUDY DESIGN	Patients who fulfill all I/E criteria will be enrolled into Study I Study Group (70 patients): Treatment Arm I - Patients will be administered one IV dose of 50U/kg of Berinert® (round to the nearest 500unit) on-call to OR for kidney transplant. Control Arm - Patients will be administered one IV dose of normal saline (NS) approximately on-call to the OR for kidney transplant in a volume identical to the volume of the IV dose of Berinert®. Berinert® (50U/kg) round to the nearest 500unit) or placebo will be administered to study subjects again at 24 hrs post-transplant.
STUDY POPULATION	 Inclusion Criteria: Adult men or women (18-70 years of age) who are on chronic dialysis therapy and acceptable candidates for receipt of a kidney transplant. Recipients of kidney allograft from ECD donors Recipients of kidney allograft from DCD donors

- Recipients of kidney allograft other than ECD and DCD who have risk index of 3-8 (minimum 3 and maximum 8) for DGF, based on the criteria in the risk index detailed in the table below
- Recipients who are ABO compatible with donor allograft
- Pre-transplant vaccination with Menactra® meningococcal vaccine
- Understand and sign a written inform consent prior to any study specific procedure

Women of childbearing potential must have a negative pregnancy test prior to randomization, and must be on an acceptable form of birth control.

Characteristic		Index
	VT2Y	THUEX
Donor Age (years)		
<40		0
41-49		1
50-54		2
55-59		3
>60		6
Cold Ischemia time		

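### The protocol gives conflicting placebo DGF rates, and the 80% power stated for 35 per arm is reached only near the lead centre's historical rates, not at the 40-50% that section 4.5.1 expects

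*Combined protocol and SAP*

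**What the plan says.** Section 6.2 lists DGF rates at the lead centre from July 2011 to July 2013: ECD 27/36 (75%), DCD 9/13 (69%), final creatinine of at least 1.5 28/37 (76%), and 33/100 (33%) for the remainder. It summarises the proposed study groups as above 70%, then says "Thus, a conservative proposal is explored below" and "We assumed a 50% DGF rate in the Placebo group". It states that 35 per group gives 80% power for a 50% reduction. On sidedness it says "A 2-sided test (to be more conservative) was performed", although a one-sided table follows. All 12 columns of the two tables hold the placebo rate at 50%; only the treated rate (20%, 25%, 30%), the power and the sidedness change.

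Section 4.5.1 says the design is powered for a 30-50% reduction and adds "since extensive DGF (40--50%) is expected in ECD and DCD recipients".

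Other figures for these donors appear elsewhere:
- Introduction, national data: "compared to 22, 28, and 41 percent of SCDs, ECDs, and donations after cardiac death patients respectively".
- Introduction, further on: up to 80% for ECD grafts, from the centre's own data.
- Synopsis, rationale: above 60% for extended-criteria and non-heart-beating donors.

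**The concern.** For a fixed relative reduction, power falls as the control rate falls, because the absolute difference shrinks. A planning rate is conservative only relative to the rate the trial will actually see. The protocol gives several answers to that question for essentially the same recipients, and the two sections that justify 35 per arm disagree: above 70% in 6.2, 40-50% in 4.5.1. Someone reading 6.2 alone would take true power to be at least the stated 80%. Someone reading 4.5.1 would see that the assumed 50% is the most favourable value in the range expected there.

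The consequence is for interpretation. If the placebo rate falls at 40-50%, a halving of DGF would more often than not be missed, and a non-significant DGF comparison could be over-read when a Phase III dose and endpoint are chosen.

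**Working it through.** **Inputs.** Two-sided alpha 0.05, continuity-corrected chi-square test, 1:1 allocation, 35 per arm, 50% relative reduction (6.2). Placebo rates from 6.2, 4.5.1, the synopsis and the introduction.

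**Step 1: reproduce the plan's tables.** With treated rate p1, placebo rate p2, d = p2 − p1 and p̄ their mean:

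m = [1.960·√(2p̄(1−p̄)) + 0.842·√(p1(1−p1) + p2(1−p2))]² / d²

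n = (m/4)·[1 + √(1 + 4/(m·d))]²

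For 50% v 25%: m = (1.960 × 0.6847 + 0.842 × 0.6614)² / 0.0625 = 57.7, so n = 14.42 × (1 + √1.277)² = 65.4, rounded up to 66. The table prints 66. The other 11 entries also reproduce, so the tables are right for their inputs. The sentence claiming 80% power with 35 per group does not follow from them: 50% v 25% needs 66 two-sided (54 one-sided). That is a separate error. It matters here because it makes the 80% claim depend on a placebo rate well above 50%.

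**Step 2: exact power at 35 per arm.** With i and j events in the treated and placebo arms and s = i + j, the corrected statistic for n per arm reduces to

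X² = 2n(|i − j| − 1)² / [s(2n − s)]

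Power is the sum of Bin(i; n, p1)·Bin(j; n, p2) over all (i, j) with X² ≥ 3.841. With p1 = p2/2:

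| Placebo rate | Where the rate appears | Power, 35 per arm | n per arm for 80% (step 1 formula) |
|---|---|---|---|
| 28% | Introduction, national ECD | 21.2% | 146 |
| 40% | 4.5.1, lower end | 35.7% | 91 |
| 45% | 4.5.1, middle | 43.0% | 77 |
| 50% | 6.2 assumption; 4.5.1, upper end | 49.8% | 66 |
| 60% | Synopsis (stated as above 60%) | 62.3% | 49 |
| 70% | 6.2, centre (stated as above 70%) | 76.9% | 37 |
| 75% | 6.2, centre ECD | 84.5% | 32 |

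Power at 35 per arm reaches 80% at a placebo rate of about 72%.

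**Step 3: does this vanish if the 35-versus-66 error is corrected?** No. At 66 per arm the same exact calculation gives 80.7% at 50%, 73.6% at 45% and 65.0% at 40%. Moving from 50% to 40% costs 14.1 points at 35 per arm (49.8 − 35.7) and 15.7 points at 66 (80.7 − 65.0).

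**Step 4: the 30% end of the effect range in 4.5.1.** Replacing n by n(1 − 1/(n·d))² in the uncorrected power formula gives approximate corrected power for a 30% relative reduction at 35 per arm: 12% at a 40% placebo rate, 17% at 50%, 34% at 70% and 40% at 75%. No rate up to 75% gives 80% power for that effect.

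**The case against.** The strongest defence is that 6.2 gives its reason. The sentence before the word conservative cites centre rates above 70% for the proposed study groups, and 50% is well below that. At 35 per arm, using 50% instead of 70% lowers computed power from 76.9% to 49.8%, so against the stated basis the choice is cautious. The national 28% and 41% are background, not a forecast for a trial that requires chronic dialysis and excludes some lower-risk kidneys. The named location and the randomising pharmacy are at the lead centre, and extension to collaborators awaits contracts. The stated primary objective is safety. All of this stands.

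It follows that a reader might infer too much in two ways. One is that 50% is the highest rate the protocol gives. It is not: 6.2, the synopsis and the introduction all give higher ones. The other is that 80% power is reached at no rate the protocol expects. That also fails, because 6.2 cites rates above 70% for the proposed study groups.

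What the defence does not answer is 4.5.1, which calls 40-50% the expectation and says the design is powered. Nor do the centre's rates settle the matter:
- The counts are small (13 DCD recipients).
- Non-ECD/DCD recipients with a risk index of 3-8 may enrol. The centre's rate in its remaining category was 33%, which is only indicative because enrolees are selected for risk.
- The dialysis endpoints exclude patients dialysed for hyperkalemia, and 6.2 does not say whether the centre's counts do.
- The introduction itself says the decision to dialyse varies between centres.

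**Conclusion.** The planning rates conflict and should be reconciled. The 50% rate is conservative relative to the lead centre's data only; relative to 4.5.1 it is the upper end. For a halving of DGF with 35 per arm, power is about 36-50% across the 4.5.1 range, 62% at 60%, and 77-84.5% at 70-75%. The stated 80%, and the claim in 4.5.1 that the design is powered, hold only near the centre's historical rates, and then only for the 50% end of its 30-50% effect range.

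These figures assume the test named in 6.2, complete data on 35 per arm, and DGF as a single binary outcome. Section 4.5.7 rules out replacing dropouts, so missing outcomes would lower power further. The documents do not show which placebo rate will occur.

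A reader might also add the centre table's rows (36 + 13 + 37 + 100 = 186), compare them with N=237, and conclude that the centre's rates are unreliable. The documents do not support that: the header says only transplants, so other categories may lie outside the rows, and a row may have been lost in the text.

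**What to change.** 1. State one expected placebo DGF rate for the population to be enrolled, with its source and DGF definition, and use it in both 4.5.1 and 6.2. Say why it differs from the national figures and from the centre's figures.
2. In 6.2, qualify conservative as relative to the lead-centre data only.
3. Replace the single 80% statement in 6.2, and the powered statement in 4.5.1 and its repeat in 4.5.7, with power at 35 per arm across placebo rates of about 30-75%. For a 50% reduction with the named test: 23% at 30%, 36% at 40%, 43% at 45%, 50% at 50%, 62% at 60%, 77% at 70% and 84.5% at 75%. Add a row for a 30% reduction if 4.5.1 keeps that range.

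This changes text and adds one small table. Enrolment, randomisation and data collection stay as they are. The only downside is that the stated power looks less favourable.
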